5.2 Study Visits and Procedures

Screening Period (-7 Days)

Eligible subjects will be asked to read and sign an informed consent and photograph consent form. No study procedures will be conducted until the informed consent and photograph consent form is signed.

At the Screening Visit, the following procedures will be performed:

- Conduct the informed consent and photography consent process.
- Record Demographics to include age, sex, and race.
- Review the inclusion/exclusion criteria.
- Record all concomitant medications including all prescription drugs, nonprescription drugs, and nutritional supplements.
- Perform a full physical examination including height (cm) and weight (kg).
- Record pertinent medical history including tobacco, illegal substance and alcohol history and current use.
- Administer the following assessments, in which only the treatment area(s) are to be evaluated: Investigator's Global Assessment (IGA) and BSA.
- Administer the Eczema Area Severity Index (EASI).

If more than 7 days is required for the subject to qualify for the study, then the subject must be screen failed, rescreened and all screening procedures repeated.

Visit 1 Baseline (Day 1)

The following procedures will be completed at Visit 1 Baseline. It is possible for the subject to be screened and complete the Visit 1 Baseline procedures on the same day.

- Review inclusion and exclusion criteria to ensure the subject qualifies for the study.
- If this visit is not combined with the screening visit:
- Perform an abbreviated physical examination including height (cm) and weight (kg)

Confidential

San Antonio, TX Protocol No. SAN007-02 Final Am 6: 18-Sept-2017

- Update concomitant medications including all prescription drugs, nonprescription drugs and nutritional supplements
- Review and update the subject's pertinent medical history.
- Administer the following assessments, in which only the treatment area(s) are to be evaluated: Investigator's Global Assessment (IGA) and BSA.
- Administer the Eczema Area Severity Index (EASI).
- Using calculated BSA, calculate Subject dose using 0.5gm per 1% BSA (i.e. 2% BSA= 2 x 0.5gm= 1gm per application)
- If subject is a female of childbearing potential, collect a urine sample and perform a β-human chorionic gonadotropin pregnancy test.
- Weigh full tube of SAN007 study medication, with cap on, and record weight prior to first dose.
- Instruct the subject on proper washing of the target treatment area(s)
 (using only study-approved cleanser) and self-application of SAN007 study
 medication, subject to apply first dose in the office.
- Assess Tolerability immediately following study drug application.
- Weigh tube of SAN007, with cap on, immediately following first application
 and record weight prior to for dose. The difference between this weight
 and the pre-application weight is to be used as the expected estimated
 usage per application. (i.e. pre-application weight- post-application
 weight = expected usage per application (EUA)
- Photograph the treatment area(s).
- Instruct the subject, when bathing, to refrain from using any body wash, lotion or moisturizer, other than that which has been provided for the treatment areas during the treatment period.
- Instruct the subject to return with the study drug in one week for the next study visit.

Visits 2 (Day 7 [±2 days]) and 3 (Day 14 [±2 days])

The following procedures will be performed during Treatment Visit 2 and Visit 3:

- Query for adverse events.
- Administer the following assessments, in which only the treatment area(s) are to be evaluated: Investigator's Global Assessment (IGA), Tolerability and BSA.

- Administer the Eczema Area Severity Index (EASI).
- Update concomitant medications including all prescription drugs, nonprescription drugs, and nutritional supplements.
- Query for treatment regimen compliance.
- Weigh and record the weight of the study medication, then re-dispense existing, or dispense a new, tube of study medication
- Calculate compliance. (i.e. visit day x 2 (applications per day) x EUA= expected usage) If Subject's actual compliance is ≤80% of expected compliance, re-educate and document in source.
- Photograph the treatment area(s).
- Review the directions for use of the study medication with the subject, and re-educate if applicable.
- (Visit 2 [Day 7 \pm 2] only) Instruct the subject to return in one week for the next study visit, with their study drug.
- (Visit 3 [Day 14 ± 2] only) Remind the subject that the next visit will be a telephone follow-up Visit 4 (Day 21 ± 2)

Visit 4 Telephone Call (Day 21 [±2 days])

The following information will be collected from the subject during the Visit 4 telephone call:

- Query for adverse events.
- Update concomitant medications including all prescription drugs, nonprescription drugs, and nutritional supplements.
- Query for treatment regimen compliance.
- Instruct subject to return to the clinic for Visit 5 Final Visit (Day 28 \pm 2), with the study drug.

Visit 5 Final Visit (Day 28 [±2 days])

The following procedures will be performed during the Final Study Visit:

- Query for adverse events.
- Update concomitant medications including all prescription drugs, nonprescription drugs, and nutritional supplements.
- Query for treatment regimen compliance.

- Collect and weigh the study medication and record the weight.
- Calculate compliance. (i.e. Visit Day x 2 (applications per day) x EUA= expected usage) If Subject's actual compliance is ≤80% of expected compliance, re-educate and document in source.
- If subject is a female of childbearing potential, collect a urine sample and perform a β-human chorionic gonadotropin pregnancy test.
- Administer the following assessments, in which only the treatment area(s) are to be evaluated: Investigator's Global Assessment (IGA), Tolerability and BSA.
- Administer the Eczema Area Severity Index (EASI).
- Photograph the treatment area(s).
- Instruct the to return to the clinic for another study visit only if study-related adverse events persist or, in the Investigator's opinion, an additional study visit is warranted to ensure the subject's safety.

Follow-up Call (Day 35 [±2 days])

The following will be asked of the subject during the follow up telephone call:

- Query for status of AD since discontinuation of study medication
 - E.g. Has your condition been stable, improved or worsened, since discontinuing study medication?

6. EVALUATION SCALES

6.1 ECZEMA AREA AND SEVERITY INDEX (EASI)

The Eczema Area and Severity Index (EASI) score is used to measure the severity and extent of eczema.

6.1.1 EASI Body Regions

The index is applied to four body regions:

- Head and neck
- Upper limbs
- Trunk
- Lower limbs

6.1.2 EASI Intensity

The intensity of eczema, and the percentage of the affected area, are calculated for each region. The intensity of eczema is rated on a four-point scale of 0-3 (none, mild, moderate, severe):

- Redness (erythema)
- Thickness (induration, population edema)
- Scratching (excoriation)
- Lichenification (lined skin)

6.1.3 EASI Subtotal of Intensity of Each Body Region

The four intensity scores are added up for each of the four regions to give subtotal (A1, A2, A3, A4). Each subtotal is multiplied by the body surface area represented by that region:

- A1 x 0.1 gives B1 (in children 0-7 years, A1 x 0/2 gives B1)
- A2 x 0.2 gives B2
- A3 x 0.3 gives B3
- A4 x 0.4 gives B4 (in children 0-7 years, A1 x 0.3 gives B1)

6.1.4 EASI Percentage Area

The percentage area affected by eczema is evaluated in the four regions of the body. In each region, the area is expressed as:

- 0-0 to <1%
- 1-1% to 9%
- 2-10% to 29%
- 3-30% to 49%
- 4-50% to 69%
- 5-70% to 89%
- 6-90% to 100%

6.1.5 EASI Calculations of Area

Each of the body area scores are multiplied by the area affected:

- B1 x (0-6) = C1
- B2 x (0-6) = C2
- B3 x (0-6) = C3
 - $B4 \times (0-6) = C4$

6.1.6 EASI Total Score

The final EASI score is:

EASI= C1 + C2 + C3 + C4.

An increase in EASI score, from Baseline, during study participation, will be recorded as an AE. A new adverse event will be opened only if the PI assesses an increase in severity from initial AE. Otherwise, the initial adverse event will remain open until resolution or study completion.

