- 1- Site staff will follow the requirements of the IRB or Ethics Review Board to obtain informed consent from the Subjects
- 2- Only pertinent medical history will be recorded for each Subject

Confidential

San Antonio, TX

Protocol No. SAN007-02

Final Am 6: 18-Sept-2017

- 3- Only complete if Screening and Baseline visit are not done together
- 4- A urine pregnancy test will be completed for all subjects of child-bearing potential at the designated study visits, or at any visit if there is suspicion of pregnancy during the treatment period.
- 5- This should be done twice at Baseline Visit, before, and after application
- 6- Additional study drug may be dispensed at each visit depending on usage
- 7- Adverse events (AE) will be collected after the Subject's first treatment at Visit 1 and throughout the trial. Record only study medication related AE at Visit 5. If AE persists after the follow-up visit, the Subject may be required to return to assess the AE.

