6.2 INVESTIGATOR GLOBAL ASSESSMENT

The Investigator Global Assessment (IGA) should be administered by the same Investigator, or designee, for any given Subject at all study visits. Any increase in IGA grade will be recorded as an AE. It will be used to measure efficacy according to the following scale:

Grade	Score	Description			
Clear	0	No inflammatory signs of AD			
Almost Clear	1	Just perceptible erythema and just perceptible population/infiltration			
Mild	2	Mild erythema and mild population/infiltration			
Moderate	3	Moderate erythema and moderate population/infiltration			
Severe	4	Severe erythema and severe population/infiltration			

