7.3.1 Treatment of New Lesions

During the Treatment Period, new lesion(s) that appear are permitted to be treated as long as they are not in a study exclusion area; however, these lesions should not be included in the EASI, IGA, or BSA assessments. Any changes in tolerability between old lesions and new should be recorded and clearly differentiated in the source records and eCRF.

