7.5 ADVERSE EVENTS

Information about all AEs, whether volunteered by the subject, discovered by investigator questioning, or detected through physical examination, or other means, will be collected and recorded on the Adverse Events page of the eCRF and followed as appropriate. Adverse events will be coded using an internationally recognized dictionary.

Medical conditions/diseases present before starting study treatment are only considered adverse events if they worsen after starting study treatment (i.e., any procedures specified in the protocol). Adverse events occurring before starting study treatment, but after signing the informed consent form, are recorded on the Medical History/Current Medical Conditions page of the eCRF.

As far as possible, each AE will also be described by:

- 1. its duration (start and end dates),
- 2. the severity grade (mild, moderate, severe)
- 3. its relationship to the study product (definitely, probably, possibly, unlikely, or not related),
- 4. the action(s) taken, and,
- 5. the outcome, as relevant.

Severity of adverse events

The investigator is to classify the severity of an AE according to the following definitions:

Mild: The Subject is aware of the signs or symptoms, which are easily

tolerated.

Moderate: The signs and symptoms are sufficient to restrict, but not prevent

usual activity.

Severe: The Subject is unable to perform usual activity.

The maximum intensity of an AE (mild, moderate, or severe) will be assessed considering the possible range of intensity of the symptom(s).

Relationship of adverse event to study treatment

The investigator is to classify the relationship of the AE to the investigational product according to the definitions outlined in Table 7-6.

The following study measurements will be reported as an AE:

- 1. Any increase in the subjects' EASI score or IGA during study participation.
- 2. A negative change in Tolerability, during or immediately after study drug application.

Table 7-6: Terms for Defining Relationship of Adverse Event to Study Product

Association	Definition	
Not related	(1) the existence of a clear alternative explanation (e.g., mechanical bleeding at surgical site) or (2) non-plausibility, e.g., the subject is struck by an automobile or develops cancer a few days after product administration.	

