8.4.5 Safety Evaluations

8.4.5.1 Adverse Events

The assessment of safety will be based mainly on the frequency of AEs.

Adverse events may be summarized by Medical Dictionary for Regulatory Activities (MedDRA) system organ class and preferred term. Adverse events will be summarized by presenting, for each treatment group, the number and percentage of subjects having any AE, having an AE in each body system and having each individual AE. Any other information collected (e.g., severity or relatedness to study medication) will be listed as appropriate.

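### Every EASI or IGA increase counts as an AE with no minimum size and no row of its own, so the any-TEAE row mixes other AEs with disease course and scoring noise

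*Protocol*

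**What the plan says.** Three places in the protocol set the rule. Section 6.1.6: "An increase in EASI score, from Baseline, during study participation, will be recorded as an AE". Section 6.2: "Any increase in IGA grade will be recorded as an AE". Section 7.5 lists among the measurements to be reported as AEs: "Any increase in the subjects' EASI score or IGA during study participation". None gives a minimum size or asks for a repeat assessment. Section 6.1.6 limits the opening of further AEs in the same subject, but not the first one.

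Protocol 8.4.5.1 plans, by treatment group, the number and percentage of subjects "having any AE, having an AE in each body system and having each individual AE". SAP 1.1.1 makes safety the primary objective and assesses it by subjects with at least one AE. SAP 7.1 treats every reported AE as treatment-emergent. Its summary (Table 14.3.1.1) has rows for any TEAE, each severity, related, serious, leading to discontinuation, and death. Neither SAP 7.1 nor Table 10.2 has a row or subset for AEs that arise from a score increase.

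Other passages limit the scope. Protocol 7.5 already counts real worsening of an existing condition as an AE: "Medical conditions/diseases present before starting study treatment are only considered adverse events if they worsen after starting study treatment". It grades severity by effect on activity; moderate means "The signs and symptoms are sufficient to restrict, but not prevent" usual activity. For new lesions, Protocol 7.3.1 says that "these lesions should not be included in the EASI, IGA, or BSA assessments". Table 5-1 footnote 7 adds: "Record only study medication related AE at Visit 5".

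**The concern.** EASI and IGA are also the efficacy measures. A subject whose EASI rises by the smallest possible step, with no complaint and no reaction, enters the any-TEAE row on the same footing as a subject with an application-site reaction. Readers will compare that row between arms even though no test rests on it. Two things can then happen. Rises common to both arms take up room in the row and shrink a real difference in other AEs. If the cream improves the disease, placebo subjects collect more score-rise events, so an efficacy effect feeds into the safety comparison.

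How many rises count is also unclear. Section 6.1.6 measures the rise from Baseline, while 6.2 and 7.5 name no reference visit. Footnote 7 restricts recording at Visit 5 to medication-related events, while 6.1.6 and 7.5 cover any rise during participation.

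**Working it through.** The documents state no AE rate, rise rate, alpha or power for this point, so there is no plan figure to reproduce. Every rate below is an assumption.

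**1. Smallest triggering step (Protocol 6.1.2 to 6.1.6).** A region contributes weight × intensity sum × area score. One intensity point at area score 1 adds 0.1 × 1 × 1 = 0.1 in head and neck, and 0.2, 0.3 or 0.4 in the other regions. Against the lowest eligible EASI of 2, 0.1 is 5%. The smallest IGA step is one full grade.

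**2. Share of subjects with at least one EASI rise over three visits (Days 7, 14, 28), no true change.**
- No ties: a subject has no rise only if Baseline is the highest of four exchangeable scores, so the rate is 1 − 1/4 = 75%. EASI has ties, so this is an upper limit.
- Scores rounded to 1, 2 or 3 error SDs, true score at random on the grid: 60%, 45%, 34%.
- Protocol EASI formula, simulated. Assumed: 30/70/50/60% of subjects affected in head-neck/upper limbs/trunk/lower limbs, area scores 1-3, signs centred on mild or moderate, median baseline about 5.4, errors independent between visits.

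| Each item misrated one step | 2% | 5% | 10% | 20% |
|---|---|---|---|---|
| EASI rise, 3 visits | 30% | 50% | 63% | 69% |
| EASI rise, 2 visits (Visit 5 rises not recorded) | 23% | 41% | 54% | 60% |
| IGA rise alone, 3 visits | 4% | 10% | 18% | 32% |

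Other assumed baselines move the three-visit EASI row by only a few points (27/47/61/68% to 32/53/65/70%). At 2% and 5% misrating, 76% and 66% of subjects with a rise have a largest rise under 1 point. That share depends on the baseline assumed; a median of 7.1 gives 67% and 56%. Misrating here means inconsistency between visits, since a constant assessor bias cancels.

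**3. With true improvement.** If every visit is better than Baseline by 1, 2 or 3 error SDs, the no-tie rate falls from 75% to 45%, 18% or 4%.

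**4. Effect on the any-TEAE row.** Let A be the share with another AE or a reaction, and r the share with a score rise among the remaining subjects. Then any-TEAE = A + (1 − A)r. Assume other AEs of 10% in both arms and reactions of 5% on placebo and 20% on active, independent of each other:
- A placebo = 1 − 0.90 × 0.95 = 14.5%; A active = 1 − 0.90 × 0.80 = 28.0%; excess 13.5 points.
- With equal r the excess is 13.5 × (1 − r): 9.5 points at r = 30% (40.2% vs 49.6%), 6.8 at 50% (57.2% vs 64.0%), and 3.4 at the 75% limit.
- The order reverses only if r placebo > 1 − (0.720/0.855)(1 − r active). That is 24%, 33% or 37% for active rates of 10%, 20% or 25%. If active reactions are 10% (excess 4.5 points), the thresholds are 15%, 24% and 29%; if 30% (excess 22.5 points), 34%, 41% and 45%.

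Using the step 2 rates as r assumes that score rises are unrelated to having another AE.

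**5. Against sampling error.** If 100 subjects split 67:33, the standard error of 28.0% − 14.5% is √(0.145 × 0.855/33 + 0.28 × 0.72/67) = 8.2 points; with 33 per arm it is 9.9. The shifts at r = 30% and 50% are 13.5 − 9.5 = 4.0 and 13.5 − 6.8 = 6.7 points.

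**The case against.** An any-TEAE row is a composite by design, and much of the detail appears elsewhere. Tables 14.3.1.2 to 14.3.1.5 show events by Preferred Term, and Table 14.3.2.1 shows discomfort. IGA improvement categories, IGA scores and EASI change by visit appear in the 14.2.2.2, 14.2.2.3 and 14.2.3.3 tables. Scores and AEs are in Listings 16.2.6.4, 16.2.6.5 and 16.2.7. True worsening would be an AE under Protocol 7.5 anyway, and new lesions are kept out of the scores. This largely stands and is why the point is small. It does not remove the point. No document says which verbatim term or Preferred Term a score rise receives, so no Preferred Term row is assured to be its own, and such a row could also hold flares reported without a score trigger. The by-visit tables use the FAS with last observation carried forward, not the Safety Set. The table shells are not available, so the finding rests on SAP 7.1 and Table 10.2.

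The assumed reaction rates are also not anchored in the documents. The wart study in Protocol 1.1 reports 4 subjects with probably or definitely related irritation against 183 completers (4/183 = 2.2%), and patch-test positivity runs from under 0.1% to 6.6%. These are other populations, but they give no support for rates of 10-30%. The example shows how the row behaves and does not forecast results.

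A separate row also does not remove noise; it only sets it apart from other AEs. That is correct, and the report should say so.

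On the reference visit, Protocol 7.3 and SAP Table 9.0 do define change against Baseline, but 7.3 is worded for efficacy and Table 9.0 is a calculation convention. Neither settles the AE trigger in 6.2 and 7.5.

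**Conclusion.** The point holds as a limited, descriptive one. Any EASI or IGA rise is an AE without a minimum size, and the summary table counts these events undivided. The effect falls mainly on the any-TEAE and mild rows. Rises from scoring noise would rarely restrict activity, and they reach the related row only if rated at least possibly related or if the rating is missing (SAP 7.1).

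Under the assumed scoring errors and no true change, roughly 30-70% of subjects would have at least one EASI rise, and far fewer if both arms improve strongly. Equal rise rates of 30-50% would reduce the example excess by 4.0 to 6.7 points, which is less than about one standard error. No test, power or sample-size figure is affected.

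Three stronger readings do not follow. A reader might infer that three quarters of subjects will have a noise AE; 75% is only the no-tie limit with no true change. A reader might infer that the arms will appear in the wrong order; that needs particular arm-specific rates, none of which the documents give. A reader might infer that score-rise events should be dropped; some will be true aggravation of treated skin, which a safety trial must show.

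**What to change.** Before unmasking, define in SAP 7.1 a flag for AEs generated only by an EASI or IGA increase, by AE term or by a blinded match of AE dates to the scores. In Table 14.3.1.1, show these events as one separate row and report any-TEAE both with and without them, keeping the protocol-defined total. State that the separate row still pools noise, disease course and true aggravation, so it is shown and not discarded. Splitting the severity and related rows is optional.

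Reconcile Protocol 6.1.6 with 6.2 and 7.5 on the reference visit, and reconcile Table 5-1 footnote 7 with 6.1.6 and 7.5 on which AEs are recorded at Visit 5.

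The cost is one derived flag, two table rows and some blinded matching, since the documents do not show that the AE page records what triggered an event. No data are removed.

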6.2 INVESTIGATOR GLOBAL ASSESSMENT

The Investigator Global Assessment (IGA) should be administered by the same Investigator, or designee, for any given Subject at all study visits. Any increase in IGA grade will be recorded as an AE. It will be used to measure efficacy according to the following scale:

Grade	Score	Description			
Clear	0	No inflammatory signs of AD			
Almost Clear	1	Just perceptible erythema and just perceptible population/infiltration			
Mild	2	Mild erythema and mild population/infiltration			
Moderate	3	Moderate erythema and moderate population/infiltration			
Severe	4	Severe erythema and severe population/infiltration			

6.3 URINE PREGNANCY TESTS

Females of childbearing potential will undergo a urine pregnancy test (UPT) at Visit 1 (Day 1) and at Visit 5 (Day 28 ±2). If the urine pregnancy test is positive at Visit 1, the subject will not be permitted to enroll in the study. Any subject who becomes pregnant during the trial must be discontinued from further treatment. If there is a suspicion of pregnancy at any time during the Treatment Period, a urine sample will be obtained and tested. All pregnancies should be immediately reported to the sponsor and medical monitor within 24 hours of awareness and followed through to resolution.

